7.1 Safety Definitions

7.1.1 Adverse Event

Any untoward medical occurrence in a patient or clinical trial subject administered a medicinal product and which does not necessarily have a causal relationship with this treatment. An AE can therefore be any unfavorable and unintended sign (including an abnormal laboratory finding), symptom or disease temporally associated with the use of the study medication, whether or not considered related to the study medication.

7.1.2 Adverse Drug Reaction

All untoward and unintended responses to an investigational medicinal product (IMP) related to any dose administered.

All cases judged by either the reporting medically qualified professional or the Sponsor as having a reasonable suspected causal relationship to the study medication qualify as adverse drug reactions.

7.1.3 Unexpected Adverse Reaction

An adverse reaction, the nature or severity of which is not consistent with the applicable product information (e.g. Investigator's Brochure for an unauthorized investigational medicinal product or summary of product characteristics for an authorized product).

7.1.4 Serious Adverse Event (SAE) or Serious Adverse Reaction

Any untoward medical occurrence or effect that at any dose results in:

- Results in death,
- Is life-threatening,
- Requires inpatient hospitalization or prolongation of existing hospitalization, (Note: Complications that occur during hospitalization are AEs. If a complication prolongs hospitalization or fulfils any other serious criteria, the event is serious. Hospitalization for elective treatment of a pre-existing condition that did not worsen from baseline is not considered to be an AE. [NB *This means that admission (i.e. inpatient, out patient, <24 hours, > 24hour) for blood transfusion does not constitute an SAE as it is for treatment of a pre-existing condition*].)
- Results in persistent or significant disability/incapacity, (Note: The term disability means a substantial disruption of a person's ability to conduct normal life functions. This definition is not intended to include experiences of relatively minor medical significance such as uncomplicated headache, nausea, vomiting, diarrhoea, influenza, or accidental trauma (e.g. sprained ankle) that may interfere or prevent everyday life functions but do not constitute a substantial disruption).
- Is a congenital anomaly/birth defect.

NOTE: *Other events that may not result in death, are not life threatening, or do not require hospitalization, may be considered a serious adverse event when, based upon appropriate medical judgment, the event may jeopardize the patient and may require medical or surgical intervention to prevent one of the outcomes listed above. Examples of such events include, but are not limited to, severe early onset reaction such as anaphylaxis, vasovagal episodes, episodes of hypotonia, hyperreactivity or hyperventilation, convulsions, etc.*

All SAEs will be reported to the Sponsor (or designee) within 24 hours of occurrence. The Sponsor (or their designee) will be responsible for reporting the AE to the appropriate regulatory authorities and the ECs within the legally specified period. It is important to distinguish between SAEs and severe AEs. Severity is a measure of intensity whereas seriousness is defined by the criteria above. An AE of severe intensity need not necessarily be considered serious. For example, a migraine headache that incapacitates a patient for many hours may be considered a severe AE, whereas a stroke that results in a limited degree of disability may be considered mild, but should be reported as an SAE.

7.1.5 Suspected Unexpected Serious Adverse Reaction (SUSAR)

A serious adverse reaction, the nature or severity of which is not consistent with the applicable product information (e.g. Investigator's Brochure for an unapproved investigational product or Summary of Product Characteristics for an approved product).

7.2 Procedures for Recording of Adverse Events

7.2.1 General

All adverse events occurring during the Study (from the timepoint of signing of the Informed Consent Form (ICF) until completion of patient's study participation or premature withdrawal) observed by the Investigator or reported by the patient, whether or not attributed to the IMP, shall be recorded in patient's medical records and on the eCRF.

The following information shall be recorded:

- description,
- date of onset and end date,
- severity,
- assessment of relatedness to the IMP,
- seriousness,
- measures taken for management of the AE,
- outcome of the event.

Follow-up information should be provided as necessary.

AEs considered as being related to the IMP as judged by a medically qualified Investigator, or the Sponsor, must be followed until their resolution or when patient's status is considered as stable. All related AEs that result in a patient's withdrawal from the Study or are present at the end of the Study, should be re-evaluated and if needed followed until a satisfactory resolution occurs.

It will be left to the Investigator's clinical judgment whether or not an AE is of sufficient severity to require termination of IMP administration. A patient may also voluntarily withdraw from IMP administration due to AEs perceived as intolerable. If either of these occurs, the patient will be given appropriate care under medical supervision until symptoms cease or the condition becomes stable.

The severity of reported events shall be assessed on the following scale:

- 1 = mild
- 2 = moderate
- 3 = severe
- 4 = life threatening
- 5 = death

The causal relationship of AEs to the IMP must be assessed by the Investigator, or by a medically qualified designee, in accordance with the following criteria:

Term	Definition
Unrelated	Clinical event with an incompatible time relationship to administration of the investigational medicinal product (IMP), and that could be explained by underlying disease or other drugs or chemicals or is incontrovertibly not related to the IMP
Possibly related	Clinical event with a reasonable time relationship to IMP administration, and that is unlikely to be attributed to concurrent disease or other drugs or chemicals
Related	Clinical event with plausible time relationship to IMP administration and that cannot be explained by concurrent disease or other drugs or chemicals

At the last scheduled visit, the Investigator shall instruct each patient to report any subsequent event(s) that the patient, or her personal physician, believes might reasonably be related to participation in this Study. The Investigator should notify the Sponsor (or designee) of any death or SAE occurring at any time after a patient has discontinued or terminated study participation that may reasonably be related to this Study.

7.2.2 *Pre-existing Conditions*

For purposes of this Study a pre-existing condition means a diagnosis, clinically significant finding, symptom, or laboratory abnormality present at baseline (Visit 1). Subsequently, during the course of the Study it shall be recorded as an AE/SAE if the frequency, intensity, or the character of the condition worsens during the study period.

7.2.3 *Overdose*

All overdoses with or without associated symptoms, should be reported as AEs on the appropriate eCRF page. An overdose is defined as a dose of 90mg or above in a 24 hour period. If sequelae meeting the criteria for a SAE have occurred in association with the overdose, the case must be reported immediately, within 24 hours. Action to be taken, if any, in event of an overdose should be discussed with the Sponsor's medical representative at the earliest opportunity. However, in animal toxicology, no adverse events have been observed following single intravenous doses of approximately 50 times the human therapeutic dose, so no specific toxicity is anticipated. There are no known antidotes to rVA576 (Coversin) and observation and supportive treatment are the only recommended measures. An assessment of whether the overdose was accidental or intentional should be recorded. If the overdose was a suicide attempt, this fact should be clearly stated. The AEs and SAEs that occur as a result of an overdose should be recorded on the eCRF.

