7.4 Expedited Safety Reporting

Any Serious Adverse Event, which is unexpected and at least possibly related to the IMP, requiring expedited reporting to the respective regulatory authority, EudraVigilance and ECs/ Institutional Review Boards (IRB) of the sites participating in this Study is subject to following timelines:

- 7 calendar days for SUSARs involving death and life-threatening events

- 15 calendar days for SUSARs involving hospitalization or prolongation of hospitalization or persistent or significant disability/incapacity or congenital anomaly/birth defect or any other significant clinical/laboratory event of major concern in the opinion of the Investigator.

Day zero (clock start) for expedited reporting purposes is the date of initial information or of the relevant follow-up information received in any form (in writing or verbally) by any personnel of the Sponsor or contracted parties including the CRO and the PVP.

All SUSARs will be reported to the respective competent authorities, ECs (IRBs) and Investigators within specified timelines in accordance with corresponding national legislation.

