4.12.1 Adverse Events

A summary overview of adverse events will be provided, which presents the number and percentage of patients from the FAS satisfying each of the following categories:

- Any AEs
- Serious AEs (SAEs)
- Drug-related AEs
- SAEs leading to death
- AEs leading to discontinuation

The number and percentage of patients with AEs, and number of AEs will be summarised by MedDRA System Organ Class, High Level Term, and Preferred Term. In this summary, any patient reporting multiple episodes of the same AE (i.e. same preferred term), will be counted once. The incidence of SAE will also be summarised. The listings will contain all data available.

The number and percentage of patients with AEs will be summarised by reported severity within each preferred term within system organ class. In this summary, any patients reporting multiple episodes of the same AE (i.e. same preferred term), will be counted once against the most severely reported category.

A list of patients reporting any SAEs and a list of patients reporting any AEs that led to an interruption or withdrawal of the study medication will be provided.

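### The three causality definitions neither cover every adverse event nor exclude one another, so the drug-related AE count rests partly on choices the criteria do not settle

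*Protocol*

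**What the plan says.** Protocol 7.2.1 requires investigators, or medically qualified designees, to assign causality by the table given there. Its three definitions are:

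- *Unrelated* has two limbs. The first is "Clinical event with an incompatible time relationship to administration of the investigational medicinal product (IMP), and that could be explained by underlying disease", where other drugs and chemicals serve equally as explanations. The second covers an event that the assessor is certain the drug did not cause: "or is incontrovertibly not related to the IMP".
- For *Possibly related*, the timing must be reasonable and the event must be one "that is unlikely to be attributed to concurrent disease or other drugs or chemicals".
- For *Related*, the timing must be plausible and no disease, drug or chemical may be able to account for the event.

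SAP 3.4.3 repeats the three labels without definitions. SAP 4.12.1 puts a row for "Drug-related AEs" in the AE overview but does not say which labels count. The changes from protocol in SAP 4.1 do not touch causality. Protocol 7.4 ties expedited reporting to an SAE "which is unexpected and at least possibly related to the IMP". Protocol 7.1.2 uses a differently worded standard: an event is an adverse drug reaction if the reporting professional or the sponsor reasonably suspects a causal link.

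**The concern.** The case the table omits is a common one in this trial. Dosing is every 12 or 24 hours (Protocol 5.2) for up to 4 years (5.3), so reasonable timing will nearly always be met. The SAP covers PNH patients only (SAP 1), and Protocol 1.1 lists haemolytic anaemia, thrombosis, impaired blood formation and abdominal pain among the features or consequences of the disease. For events of this kind, disease is often a credible cause alongside the drug.

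Little else in the AE analysis helps with attribution. The study is open-label with no comparator, every AE counts as treatment-emergent (SAP 3.4.3), and there is no data safety monitoring board (SAP 4.14). Three things use the investigator's label: the drug-related row, the expedited-reporting trigger, and the duty in 7.2.1 to follow related AEs until they resolve or stabilise. If the criteria do not determine the label, these inherit the ambiguity.

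**Working it through.** The plan states no figure on this point, so the check is logical. Each definition was treated as a condition on three facts: timing (compatible or not), other explanation (credible, unlikely, or impossible), and whether the event is certainly not due to the drug. Reasonable and plausible timing are taken as the same, because the protocol does not distinguish them.

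The mix of and/or in *Unrelated* can be read in three ways:

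- A: (incompatible timing and another explanation) or certainty.
- B: incompatible timing and (another explanation or certainty).
- C: every *and* loosened to *or*.

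For events that are not certainly unrelated:

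| Timing | Other explanation | A | B | C |
|---|---|---|---|---|
| Compatible | Credible | none | none | Unrelated |
| Compatible | Unlikely | Possibly | Possibly | Possibly |
| Compatible | Impossible | Possibly and Related | Possibly and Related | Possibly and Related |
| Incompatible | Credible | Unrelated | Unrelated | Unrelated |
| Incompatible | Unlikely | none | none | Unrelated |
| Incompatible | Impossible | none | none | Unrelated |

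Three results follow.

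1. **Gap.** In the first row, both literal readings (A and B) give no category, and the loose reading gives *Unrelated*. No reading gives *Possibly related*.
2. **Overlap.** In the third row, every reading gives two categories, because a cause that cannot explain an event is also an unlikely cause of it.
3. **Second gap.** Under A and B, incompatible timing without a credible other cause has no category. With near-continuous dosing this should be rare.

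**Side by side with 7.1.2.** In a first-row event the drug may be reasonably suspected, which satisfies 7.1.2, while disease remains a credible cause, which fails *Possibly related*. Nothing in the protocol links or ranks the two standards.

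**Illustration on assumed figures.** The overview in SAP 4.12.1 counts patients. Take 50 patients (the approximate planned number), assume 10 have an undisputed drug-related AE, and let x be the number whose only candidate is a gap event. If gap events are called *Unrelated*, the row shows 10/50 = 20%. If they are called *Possibly related*, it shows (10 + x)/50:

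- x = 2: 12/50 = 24%
- x = 5: 15/50 = 30%
- x = 10: 20/50 = 40%
- x = 15: 25/50 = 50%

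The shift is x/50. The documents give neither x nor the 10.

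**The case against.** Several stronger inferences are tempting, and the case against them is good.

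- **Any event PNH might explain is barred from *Possibly related*.** The wording does not go that far. It asks whether disease is an unlikely cause, so an event that PNH might explain but probably does not still qualifies. Only events with a credible competing cause fall in the gap. Infection is a poor example, since Protocol 4.3.1 names *Neisseria* infection as a hazard of blocking C5.
- **SUSARs will be undercounted.** This is not shown. Protocol 7.3 sends every SAE to the pharmacovigilance provider whatever its causality. Protocol 7.1.2 lets the sponsor as well as the reporting professional judge an event to be a reaction, and 7.1.5 defines a SUSAR as a kind of serious adverse reaction. What remains is that 7.4 uses the table's own term as its trigger, and that these safeguards do nothing for non-serious AEs.
- **The primary safety result is compromised.** The primary endpoint has no causality element. Thrombotic and haemolytic events and MAVEs are summarised whatever the label (SAP 4.12.5 and 4.12.6), all safety data are listed, and no decision rule uses the drug-related row.
- **The row moves by the share of AEs in the gap.** The documents give no such share. A patient with another drug-related AE is already counted, so a share of AEs does not convert into a share of patients.
- **Sites will diverge.** Protocol 8 says eCRFs follow CRO guidelines, which are not among the documents. They may set a default, and investigators may use *Possibly related* despite the wording.

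These points limit the consequences. They do not give a first-row event a category.

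**Conclusion.** The point holds as a defect in the definitions. They are neither exhaustive nor mutually exclusive, and they conflict with the standard in 7.1.2. On the literal text, an event with reasonable timing and a credible other cause cannot be called *Possibly related*. It will be assigned by a choice the criteria do not settle, or left out of the drug-related row. Undercounting is one possible result, not a certain one.

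The reach is limited to the drug-related row, the follow-up duty for related AEs and, more weakly, the wording of the expedited-reporting trigger. Overall AE and SAE incidence is untouched. The size cannot be derived from the documents; the 20% to 50% range in the illustration is only an example. The conclusion assumes that investigators apply the criteria as 7.2.1 requires and that no unseen guideline closes the gap. The change is worth making because it is cheap and attribution has little other support in this single-arm trial.

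**What to change.** 1. **Reword the table in Protocol 7.2.1.**
   - *Possibly related*: reasonable timing, and the drug is a reasonable possible cause even though disease or other drugs may also explain the event.
   - *Related*: plausible timing with no other likely explanation.
   - *Unrelated*: incompatible timing, or a clearly established other cause.

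   Requiring the drug to be a reasonable possible cause keeps *Possibly related* from becoming the default for every well-timed event. Run the new wording through the grid above, and name in the eCRF guideline the category for any event that still fits none.
2. **Align 7.1.2, 7.2.1 and 7.4** so that one causality standard governs all three.
3. **State in SAP 4.12.1** that drug-related means *Possibly related* plus *Related*.
4. **Handle AEs already classified.** Re-query causality for all earlier AEs, or present AEs before and after the amendment separately. Re-querying SAEs alone would leave the row mixing two definitions for non-serious AEs.

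The cost is an amendment to the table, an update to the eCRF guideline, a sentence in the SAP and some re-query work. More AEs will be counted as drug-related, and the report should say that this follows from the definition.

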frequency become desirable, the responsible investigator will have discretion to alter the treatment regime in consultation with the Sponsor's medical representative. During any such changes careful monitoring of complement inhibition is mandatory and this should include regular assessment of haematological/biochemical parameters (e.g. serum LDH) and CH50 as well as the patient's clinical status.

In the event of an increase of dose or dose frequency, an ablating dose (AD) may be given to ensure complete complement inhibition before the new dose is started. It is assumed that a reduction of dose or dose frequency would only be considered if the patient's prior complement control was adequate and so no AD need be given before commencing the new dose.

The ablating dose (AD) consists of 2 doses; an initial dose of 60mg followed 12 hours later by 1 dose of 30mg. A suggested regimen to be followed in the event of an inadequate response to rVA576 (Coversin) treatment is given below:

PNH patients

Ablating Doses (if required)			
Dose		Interval	
60mg		Single dose	
30mg		1 x 12 hourly dose	
Inadequate Response			
Existing		Switch to	
Dose	Interval	Dose	Interval
15mg	12 hourly	22.5mg	12 hourly
22.5mg	12 hourly	45mg	24 hourly
30mg	24 hourly	45mg	24 hourly
45mg	24 hourly	22.5mg	12 hourly

aHUS patients

Ablating Doses (if required)	
Dose	Interval
60mg	Single dose
30mg	1 x 12 hourly dose
Inadequate Response	

	Existing		Switch to	
	Dose	Interval	Dose	Interval
	30mg	12 hourly	After assessment decision will be made in collaboration with the Sponsor and PI.	
	45mg	24 hourly	30mg	12 hourly
Duration of Treatment:	
Up to 4 years
 
Patients for whom rVA576 (Coversin) was found to be effective in this clinical trial and who wish to continue on the drug following conclusion of this trial, will continue to receive rVA576 (Coversin), subject to approval of the applicable governmental agency, until rVA576 (Coversin) receives marketing approval or another treatment of benefit becomes available. If Akari encounters any issues with the availability of the drug, it will allocate available drug to such patients in a manner which is fair and consistent with ethical requirements.
			

1. Introduction

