5.10 Missed doses

For PNH patients:

For a missed dose of more than >24 hours, the sample for PD (CH50) analysis should be taken if possible just prior to the next morning dose of rVA576 (Coversin). As the CH50 results will not be available for some days the Investigator should be guided by the history, clinical signs or platelet count and LDH. In some cases, the PI may feel that an ablating dose is not required and the patient should resume their usual dosing schedule as soon as possible. In PNH, clinical signs of intravascular haemolysis following resumption of dosing mandates re-initiation of the AD schedule. The CRO and the Sponsor should be informed as soon as possible.

Dose	Interval	Missed Dose <4hr	Missed Dose <24hrs	Missed dose by day(s)>24hrs
15mg	12 hourly	Dose to be taken as soon as patient realizes	Take 15mg dose immediately and 15mg dose at usual time	Take ablating dose 60mg/30mg. then take dose as per usual routine
22.5mg	12 hourly		Take 22.5mg dose immediately and 22.5 mg dose at usual time	
30mg	12 hourly		Take 30mg dose immediately and 30mg dose at usual time	
30mg	24 hourly		Take 45mg dose immediately and 45mg dose at usual time	
45mg	24 hourly		Take 45mg dose immediately and 45mg dose at usual time	

For aHUS patients:

In the event of one missed dose (defined as a dose not taken within a one-hour time window either side of the specified time) the following procedure should be adopted by the patient:

- Take the appropriate dose as per the day of the protocol as soon as possible and then resume the usual dosing schedule at the specified times

In the event of more than one missed dose the CRO and the Investigator's clinic should be informed as soon as possible and the following procedure should be adopted:

- Take 60 mg Coversin followed by 30 mg 12 hours later and then resume the usual dosing schedule (i.e. between 07:00 and 11:00 hrs daily) at the first time point after the ablation doses.

The Investigator's clinical staff should arrange for a Central laboratory blood draw for PK/PD to be taken 3 days \pm 1 day after first becoming aware of the missed doses in this situation.

The sample for PD (CH50) analysis should be taken just prior to dosing with rVA576 (Coversin).

As the CH50 results are unlikely to be available for some days the Investigator should be guided by the history, clinical signs or platelet count and LDH as to whether it is necessary to administer additional Ablating Doses.

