6.5 Interruption of Treatment

If treatment is interrupted, either for reasons outside the patient's or the investigator's control or because it is considered to be in the patient's best interest it may be resumed at the discretion of the investigator and Sponsor. Any interruption of >24 hours will require an ablating regimen of 60mg followed by 30mg 12 hours later before resuming normal dosing, this should be discussed with the Sponsor. In the event of an interruption of treatment of >28 days, the investigator should discuss with the Sponsor the advisability of resuming treatment.

7 Safety Reporting

All AEs occurring from the signing of the voluntary Informed Consent Form (ICF) to the end of the trial visit will be recorded. All adverse events, whether or not considered to be related to the study drug, will be monitored and reported at all stages of the study. Adverse events occurring between clinic visits will be reported by the patient or recorded at the next clinic visit and entered on the adverse event form of the case report forms. All adverse events must be fully recorded in the patient notes throughout the entire study period and will be transcribed into the subject's eCRF.

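### The protocol's own 60 mg + 30 mg ablating regimen meets its definition of overdose, so symptom-free dosing given as directed becomes a reportable adverse event

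*Protocol*

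**What the plan says.** Protocol section 7.2.3 sets an inclusive threshold: "An overdose is defined as a dose of 90mg or above in a 24 hour period". It then says: "All overdoses with or without associated symptoms, should be reported as AEs on the appropriate eCRF page". For each case it adds: "An assessment of whether the overdose was accidental or intentional should be recorded".

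The synopsis (Treatment Regimen) defines the ablating regimen: "The ablating dose (AD) consists of 2 doses; an initial dose of 60mg followed 12 hours later by 1 dose of 30mg". Table 7 in section 5.2 repeats it. The protocol calls for it in these situations:

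- **Interruption of treatment (6.5):** "Any interruption of >24 hours will require an ablating regimen of 60mg followed by 30mg 12 hours later before resuming normal dosing".
- **PNH dose missed by more than 24 hours (5.10):** the table entry is "Take ablating dose 60mg/30mg. then take dose as per usual routine". The text above the table allows a waiver: "In some cases, the PI may feel that an ablating dose is not required".
- **Haemolysis after dosing resumes (5.10, PNH):** "clinical signs of intravascular haemolysis following resumption of dosing mandates re-initiation of the AD schedule".
- **Dose increase (synopsis and 5.2):** the regimen may be given but is not required.

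For a delay of less than 24 hours, the PNH table in 5.10 tells a patient on 45 mg 24-hourly to take 45 mg at once and 45 mg again at the usual time.

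AEs are the first component of the primary endpoint (Protocol 3.2.1, SAP 2.4.1). SAP 3.4.3 treats every AE recorded under AK581 as treatment-emergent. SAP 4.12.1 tabulates AEs by system organ class, high level term and preferred term.

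**The concern.** An overdose rule should pick out dosing that departs from what was intended. Here the same protocol that directs 60 mg and then 30 mg also classes that total as an overdose, and it removes the safeguard of requiring symptoms. A site following both instructions would have to report an AE for a patient who did what was asked and felt nothing.

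Each such record would need a severity grade and a causality assessment (7.2.1), although nothing untoward need have happened. It would then enter the primary safety summaries with true overdoses. If some sites follow the text and others use common sense, identical dosing will be recorded differently between sites.

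**Working it through.** **Inputs**

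- Threshold: total dose of at least 90 mg in 24 h (Protocol 7.2.3).
- Ablating regimen: 60 mg at 0 h and 30 mg at 12 h (synopsis; Table 7).
- Catch-up for 45 mg 24-hourly: 45 mg at once and 45 mg at the usual time (5.10, column for delays under 24 h).
- Maintenance doses in the PNH dose schedule: 15 or 22.5 mg 12-hourly, 30 or 45 mg 24-hourly (Table 7).

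The plan gives no derived figure to reproduce, because 90 mg is a definition. The check is whether total dose over any 24 h is at least 90 mg. The window includes its starting point but not a dose exactly 24 h later.

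**Step 1: ablating regimen.** 60 + 30 = 90 mg, elapsed time 12 h. Since 90 ≥ 90, the definition is met.

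**Step 2: catch-up for 45 mg 24-hourly.** 45 + 45 = 90 mg. A separate column covers delays under 4 h, so the delay here is at least 4 h. The next usual dose then follows within 24 − 4 = 20 h. The definition is met.

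**Step 3: maintenance dosing at exact spacing.**

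- 15 mg 12-hourly: 15 + 15 = 30 mg
- 22.5 mg 12-hourly: 22.5 + 22.5 = 45 mg
- 30 mg 24-hourly: 30 mg
- 45 mg 24-hourly: 45 mg

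None reaches 90 mg. The conflict lies in the supplementary dosing that the protocol directs, not in routine treatment.

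**Step 4: status of each trigger.**

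| Situation | Status of 60 + 30 mg | Symptom-free? |
|---|---|---|
| Interruption > 24 h (6.5) | Required | Can be |
| PNH dose missed > 24 h (5.10) | Directed unless the investigator waives it | Can be |
| Haemolysis after resumption (5.10) | Mandated | No, the patient already has a disease event |
| Dose increase (5.2) | Optional | Can be |

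**Step 5: search for an exemption.** Section 7.2.3 is fully readable and contains none. Elsewhere the protocol writes its exemptions out: admission for transfusion is not a serious AE (7.1.4), and expected injection site reactions below grade 2 are not reported. It then says all other AEs are reported whatever their grade. Other parts of the protocol are redacted and could not be checked.

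**The case against.** **The rule could be read more kindly.** An AE is an untoward occurrence (7.1.1), and a directed dose is not untoward. But 7.2.3 is the more specific text, and it makes symptom-free overdoses AEs. Reading the threshold as a single administration of 90 mg is strained, because it leaves the 24-hour wording with no work to do.

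**The effect may be small.** This stands. Patients roll over on an existing dose, some ablating use is optional or waivable, and no frequency is given. Over-recording is also the cautious direction for a safety study.

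**Records could be told apart.** This largely stands. A reader might infer that directed and undirected doses cannot be separated. The documents do not support that. The eCRF is not among them, and they provide for AE description and management (7.2.1), the last dose before the event (SAP 3.4.3), dosing diaries (6.4) and missed doses (SAP 3.5). The accidental-or-intentional assessment alone does not identify a directed dose, but it is not the only information.

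**Two wider readings are tempting.**

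- A reader might count three of the five catch-up rows in 5.10 as reaching 90 mg. For 30 mg 24-hourly that relies on a printed 45 + 45 mg entry that may be a misprint or an artefact of reading the table; at the patient's own dose it is 30 + 30 = 60 mg. For 30 mg 12-hourly it needs a third, scheduled dose (3 × 30 = 90 mg), and that regimen is absent from the PNH schedule in Table 7. Only the 45 mg 24-hourly row is undisputed.
- A reader might add that routine 45 mg daily dosing becomes an overdose when a dose is taken minutes early. That presses the wording too hard, and the point does not need it.

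The protocol's aHUS rules for missed doses and rescue therapy also reach 90 mg, but SAP section 1 says no aHUS patients will enter.

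**Conclusion.** The conflict is real and follows from the text alone. The ablating regimen meets the overdose definition exactly, the 45 mg 24-hourly catch-up does too, and the readable text exempts neither. Followed literally, 7.2.3 turns compliant, symptom-free dosing into treatment-emergent AEs in the primary safety tables.

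The conclusion takes the 24-hour period as elapsed time. If a site counted by calendar day, an ablating regimen begun before noon would still total 90 mg on one day; a later start would split it 60 and 30. The 45 + 45 mg catch-up would fall on one day only if the late dose were taken after midnight.

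The effect on the tables cannot be sized. One affected patient is 1/50 = 2.0% of a 50-patient analysis set, but the number affected is unknown and may be zero, and the SAP says only up to approximately 50 patients. A reader might infer that AE rates will be materially inflated, or that such records already exist; the documents show neither. They show what the rule requires, not what sites did. A row of the AE overview would change only for a patient with no other AE of that kind. All analyses are descriptive, so no test or error rate is affected.

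**What to change.** Add a sentence to Protocol 7.2.3, for example: *Ablating and missed-dose dosing given as this protocol directs (sections 5.2, 5.10 and 6.5) is not by itself an overdose or an adverse event; any associated symptoms are reported as adverse events.* Identify any such records already entered, so that the AE summaries can show them separately from true overdoses.

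No dose or threshold needs to change. Moving the threshold to strictly above 90 mg would be a weaker remedy. If the first maintenance dose, 24 h after the 60 mg dose, is counted in the same period, the total is again over the limit: 60 + 30 + 15 = 105 mg for 15 mg 12-hourly, and 60 + 30 + 45 = 135 mg for 45 mg 24-hourly.

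The cost is a minor protocol amendment with its approvals, and a check of the AE records for overdose entries.
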